Specific Aim 1 is to determine whether patients with asymptomatic carotid stenosis will differ in cognitive function compared to age-matched individuals without carotid stenosis but with similar vascular risk factors. The primary hypothesis is that in patients with asymptomatic carotid stenosis ($\geq 50\%$ diameter-reducing) who survive stroke-free for 2 years; the change in overall and domain-specific cognitive function will be significantly different compared to those without stenosis. The primary analysis of impact will be the overall and domain-specific cognitive change score at 2 years, with the initial score at recruitment serving as the baseline.

Patient recruitment

Eligible patients are defined as having asymptomatic $\geq 50\%$ diameter reducing carotid stenosis. Asymptomatic status in patients will be confirmed by a history, physical examination, and numeric NIH Stroke Scale96 as defined in prior NIH carotid trials1-4. While asymptomatic patients with diameter stenosis $\geq 60\%$ benefit from revascularization2, that benefit is reduced when compared to symptomatic patients1, 4. Most centers including

ours, follow the common practice of operating on symptomatic patients with stenosis, but only consider revascularization for asymptomatic patients when the stenosis is >80%^{45, 46}. In this standard of care approach, asymptomatic patients with moderate carotid stenosis (50-80%) are treated medically and followed with annual screening studies to monitor for disease progression. Once a decision has been made that they do not require revascularization, these patients will be recruited to our proposed study. The decision as to whether a subject is appropriate to be followed with medical management alone will be made by the treating clinician in consultation with their patient. Participation in this study will not require any change in the standard clinical care that patients receive.

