Conduct of testing. In Specific Aim 1 the primary hypothesis is that in patients with asymptomatic carotid stenosis ($\geq 50\%$ diameter-reducing) who survive stroke-free for 2 years; change in overall and domain-specific cognitive function will be significantly different compared to those without stenosis (fig 1 and 3). The primary analysis of impact will be the overall and domain-specific cognitive change score at 2 years, with the initial score at recruitment serving as the baseline. Patients and control subjects will undergo a 50-minute neurocognitive battery at 3 time points: baseline, 1 year, and 2 years after recruitment. Baseline testing will take place within a few days of recruitment. Following the approach of our prelim data #3 for performing cognitive testing in a similar patient population, the battery will consist of 10 standardized neuropsychological tests for multiple cognitive domains selected on the basis of the NIH harmonization standards, our own preliminary data #3, and published experience in patients with carotid stenosis^{5-10, 31}. All tests have published age-adjusted norms. All participants will undergo all 10 tests. The order of test administration will remain constant for baseline and follow-up evaluations. Tests will be conducted in a quiet room. The order of administration accommodates the delays required for recall intervals and minimizes stimuli interference in memory tasks.

Plaque architecture and composition

The architecture and composition of plaques may influence the risk and quantity of atheroembolization, and the nature and extent of microembolic cerebral injury (fig 1). Specific Aim 2a of our study will investigate whether cognitive impairment is mediated by plaque features that predispose it to rupture and atheroembolization. Specifically, we will test whether A) at 2 years, carotid plaque architecture and composition will independently predict a change in cognitive function and, B) at 2 years, patients with asymptomatic carotid stenosis who develop cognitive impairment will differ in these characteristics compared with similar patients that remain unchanged.

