Specific Aim 1 of the study will assess whether in patients with asymptomatic carotid stenosis $\geq 50\%$ who survive stroke-free for 2 years, change in overall and domain-specific cognitive function will be significantly different compared to those without stenosis. We will confirm the group distribution of demographic variables.

Additional analyses will be performed after correction for the age, education and mood status of patients. This hypothesis will be examined with analysis of covariance comparing the composite change scores for patients versus non-stenosed control groups at the 2-year time point after adjustment for the baseline cognitive function score. Although we anticipate the level of missing data due to missed visits to be modest, these analyses will be conducted using the mixed modeling approaches of Laird and Ware.

Specific Aim 2 (a through d) is designed to identify potential mechanisms of cognitive change in patients with asymptomatic carotid stenosis. We hypothesize that carotid plaque architecture, plaque composition, microembolic counts, serum pro-inflammatory markers, and cerebral hypoperfusion could each mediate cognitive decline. Within this aim, there are 2 hypotheses for each mechanism:

A) At 2 years, the features listed above will independently predict a change in cognitive function. The statistical approach for this aim will be identical to that of the hypothesis in specific aim 1. Associations with cognitive

change scores and plaque area, volume, composition, microembolic counts, serum pro-inflammatory marker levels and cerebrovascular reactivity will be assessed using the mixed models of Laird and Ware106. Power to detect associations of cognitive decline with each of these features can be estimated using the same approaches as for the hypothesis in aim 1. We have used the most conservative approach of dichotomizing these continuous variables at their median value – the actual analysis will be performed using the variables as continuous measures where the power will be greater. Using this very conservative approach for power calculations, the same detectable differences in change score of 0.4 SD with 90% power, and of 0.3 SD with 80% power, are achievable.

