B) At 2 years, patients with asymptomatic carotid stenosis who develop cognitive impairment will differ in these characteristics compared with similar patients that remain unchanged. The differential mean value for plaque area, volume, composition, microembolic counts, serum pro-inflammatory marker levels and cerebrovascular reactivity will be tested between the two groups using t-tests. The detectable difference for each of these factors is again very conservatively estimated to be the same differences of 0.4 SD with 90% power, and 0.3 SD with 80% power (now the SD of each of these factors). Such a small change relative to the SD of each of these factors is reasonable to define as being small enough to detect all “clinically important changes.”

Specific Aim 3 is designed to explore whether cognitive changes in patients with asymptomatic carotid stenosis correlate with changes in health-related quality of life. We hypothesize that at 2 years, regardless of plaque features, cognitive change will correlate with change in health-related quality of life measures.

For this aim, the principal outcome variables will be the change in quality of life measures (Frenchay and SF-36) between baseline and follow-up. The outcome event will be cognitive change score at the corresponding follow-up time point. Initially, the correlation between each quality of life change score and corresponding cognitive change score will be explored in a univariate fashion using t-tests. Subsequently, multivariate analysis will be used to determine the independent impact of altered cognition on quality of life after controlling for additional patient variables such as age, gender, mood, medical co-morbidities, and degree of stenosis. Independent predictors of change in quality of life will be selected based on $p \leq 0.05$. With the sample size of 142, a correlation of 0.2 between change in cognitive function and change in quality of life can be detected with 90% power, and a correlation of 0.18 can be detected with 80% power.

Potential difficulties and Alternate approaches/analyses:

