Practice effect on cognitive testing. Since patients will be exposed to the same cognitive tests at different periods, scores may improve due to the “practice effect.” In this study, the practice effect is anticipated to be low since tests are being repeated at 1 year intervals (baseline, 1 year, and 2 years post-recruitment). Alternate test forms will be used wherever possible. Reliable change analyses will be used to determine if changes detected in the composite score, as well as on specific domain scores of interest exceed that which is expected based on repeated exposure to the measure, error variance, and maturation.

Additional analysis of Aim 1 including patients with post-recruitment stroke. Based on prior randomized trials, it is anticipated that approximately 1-2% of our patients per year will suffer a stroke2. Separating primary cognitive deficits from poor performance on cognitive testing due to disability associated with stroke is difficult. Furthermore, patients that develop stroke during follow-up will require carotid revascularization with elimination of the stenosis per standard of care. That is why the proposed study will exclude such patients when evaluating cognitive outcome. This attrition has been accounted for in the power analysis, and will not affect our results. Moreover, for those unable to complete testing due to stroke, the statistical E-M algorithm (Laird and Ware106) will be used to provide an estimate of the mean score in the presence of the missing data. This statistical approach has been shown to produce unbiased estimates that are more precise than alternative approaches in the presence of data that are missing.

Additional analysis of Aim 1 comparing baseline cognition in the two groups. We feel that a major strength of the application is the longitudinal data collection and comparisons of change scores. This is statistically much more powerful than a simple cross-sectional comparison. However, we will have data on baseline cognitive scores for patients versus control subjects. In an additional analysis we will perform a simple comparison of these scores to measure differences at baseline in the two populations.

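### Aim 1 makes the overall and domain-specific change scores jointly primary with no success rule, while the power and analysis text cover a single composite score

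*Combined protocol and SAP*

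**What the plan says.** In the combined protocol and SAP, under Justification, Objective, & Research Design (item 2, Specific Aim 1), the endpoint sentence reads: "The primary analysis of impact will be the overall and domain-specific cognitive change score at 2 years". Study Procedures (item 2, Conduct of testing) repeats it.

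The hypothesis has the same joint form, that "change in overall and domain-specific cognitive function will be significantly different compared to those without stenosis". It appears in Justification items 1 and 2, Supporting Literature item 1, Study Procedures item 2, and Sample Size and Data Analysis item 2.

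The analysis text is narrower. In Sample Size and Data Analysis (item 2, Specific Aim 1): "This hypothesis will be examined with analysis of covariance comparing the composite change scores", at 2 years and adjusted for baseline score. The Power Analysis in item 1 uses a t-test on one cognitive change score. It aims at 0.4 SD and takes its clinically important difference from a composite.

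On the domains, Conduct of testing says only that "the battery will consist of 10 standardized neuropsychological tests for multiple cognitive domains". The paragraph on practice effect applies reliable change analyses to the composite "as well as on specific domain scores of interest exceed that which is expected" from repeat exposure, error variance and maturation. It does not say which domains are of interest.

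**The concern.** The endpoint wording puts several scores at the same rank, and the analysis wording tests one. Nothing states whether Aim 1 succeeds on the composite, on any score, or only if all scores differ. The plan therefore leaves room to report a primary finding on one domain when the composite, which carries the power calculation, shows no difference.

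The open domain list adds to this. Under Monitoring Plan - Individual, the principal investigator reviews primary and secondary outcomes and preliminary analyses twice a year. A domain set fixed after such a review would not be pre-specified.

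**Working it through.** **Inputs from the documents.** 142 patients and 142 controls; target difference 0.4 SD (Power Analysis); 90% power (Justification item 1; the 0.4 SD and 90% pair is stated under Aim 2 in the analysis plan). Number of domains, their correlation, and alpha for Aim 1: not given. The only significance threshold in the analysis plan is p ≤ 0.05 for choosing predictors in Aim 3.

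**Assumptions.** Two-sided 5% for each test; K domains with equal pairwise correlation r; composite equal to the standardised mean of the domains; no true difference on any score.

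**Step 1: the plan's power figure.** Power = Φ(d·√(n/2) − z). With d = 0.4 and n = 142, 0.4 × √71 = 3.370; 3.370 − 1.960 = 1.410; Φ(1.410) = 92.1%. The exact t-test gives 91.9%. The 90% requirement needs 132 per group, so 142 leaves room for about 7% attrition (1 − 132/142). The sample size fits one unadjusted two-sided 5% comparison. (The companion figure of 0.3 SD at 80% does not reproduce two-sided: power is about 71%. That is a separate matter.)

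**Step 2: false-positive rate if any one score may count.** The K domain z-scores were simulated 400,000 times per setting, with composite = mean ÷ √[(1 + (K − 1)r)/K]. The table gives the proportion of draws in which the composite or any domain exceeded 1.96 in absolute value.

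| K | r = 0 | r = 0.3 | r = 0.5 | r = 0.7 | r = 0.8 |
|---|---|---|---|---|---|
| 3 | 16.0% | 14.4% | 12.9% | 11.0% | 9.9% |
| 4 | 20.4% | 18.0% | 15.9% | 13.1% | 11.5% |
| 5 | 24.5% | 21.5% | 18.5% | 14.9% | 12.8% |
| 6 | 28.2% | 24.4% | 21.0% | 16.4% | 13.9% |
| 10 | 41.6% | 35.1% | 28.7% | 21.3% | 17.4% |

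Hand check at r = 0: the rate must lie between 1 − 0.95^K and 1 − 0.95^(K+1). For K = 4 that is 18.5% to 22.6%, and for K = 6 it is 26.5% to 30.2%. The simulated 20.4% and 28.2% fall inside.

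**Step 3: a domain significant while the composite is not.** The composite alone contributes 5%, so this probability is the table entry minus 5 points. For K = 4-6 and r = 0-0.7 it runs from 13.1 − 5 = about 8% to 28.2 − 5 = about 23%.

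**Step 4: the other readings.** If only the composite is tested, the rate is 5%. If every score must be significant, it cannot exceed 5%, and the loss falls on power.

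**Step 5: what the sample size can support.** With the composite as sole primary, power stays at 91.9%. If all scores stay primary with Bonferroni adjustment, exact-t power per score at 0.4 SD falls to 78.1% (5 tests), 76.2% (6) or 74.5% (7). Restoring 90% would take 193 per group for 6 tests or 198 for 7, before attrition.

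**The case against.** The best reply is that the operative text already points to the composite. The analysis plan says the hypothesis is examined by "comparing the composite change scores for patients versus non-stenosed control groups at the 2-year time point", the power calculation concerns one score, and no between-group test of domain scores is specified. On that reading the error rate is 5% and the domain wording is only descriptive. This is a reasonable reading and probably the intended one, but the documents never say it, and the hypothesis introduced just before that analysis still includes the domains.

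A reader might infer more: that a significant result on any single domain satisfies the primary hypothesis, so that the study's false-positive rate is 13-28%. The documents do not support that. No section states such a rule, and the word joining overall and domain-specific function can equally be read as requiring both. The figure also depends on a domain count, correlations and an alpha that the plan does not give. Its upper end needs uncorrelated domains, which is unlikely for scores from one battery in the same people.

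The reliable change analyses do not close the gap, because they deal with practice and measurement error within a person. The separately uploaded protocol file and the figures were not available and may hold a domain list or a testing rule. The text reviewed here would still need to agree with it.

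**Conclusion.** The defect is a mismatch between the endpoint and the analysis, together with a missing success rule. It is not an established error rate. Aim 1 ranks the composite and an unlisted set of domains equally, while the power and the analysis cover one score.

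Inflation arises only if any one score may count as success. In every setting computed it is then about twice the assumed 5% or more: about 13-28% for 4-6 domains with r = 0-0.7, and about 10-42% for 3-10 domains with r = 0-0.8. These are illustrations under two-sided 5% tests and equal correlations. The stated 90% power holds for a composite-primary design. It does not hold if all scores stay primary with Bonferroni adjustment over 5-7 tests.

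**What to change.** State that the 2-year composite change score is the single primary outcome, tested at two-sided 5%. Make the change everywhere the joint wording stands: Justification items 1 and 2, Supporting Literature item 1, Study Procedures item 2, and Sample Size and Data Analysis item 2. Changing only some of these would leave the contradiction in place.

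List the domain scores and how each is built from the 10 tests, and make them secondary. Either of two treatments would do: Holm-adjusted tests, confirmatory only if the composite is significant; or estimates with intervals, labelled descriptive.

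Issue this as a dated clarification that says whether outcome data had been seen. The VA-Specific Criteria section says recruitment is closed, and the monitoring plan allows review of outcomes and preliminary analyses, so a reader will need to know.

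The cost is a stricter standard for single-domain claims. No participants or procedures are added, and composite power is unchanged at about 92% for 0.4 SD with 142 per group.

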Specific Aim 1 of the study will assess whether in patients with asymptomatic carotid stenosis $\geq 50\%$ who survive stroke-free for 2 years, change in overall and domain-specific cognitive function will be significantly different compared to those without stenosis. We will confirm the group distribution of demographic variables.

Additional analyses will be performed after correction for the age, education and mood status of patients. This hypothesis will be examined with analysis of covariance comparing the composite change scores for patients versus non-stenosed control groups at the 2-year time point after adjustment for the baseline cognitive function score. Although we anticipate the level of missing data due to missed visits to be modest, these analyses will be conducted using the mixed modeling approaches of Laird and Ware.

Specific Aim 2 (a through d) is designed to identify potential mechanisms of cognitive change in patients with asymptomatic carotid stenosis. We hypothesize that carotid plaque architecture, plaque composition, microembolic counts, serum pro-inflammatory markers, and cerebral hypoperfusion could each mediate cognitive decline. Within this aim, there are 2 hypotheses for each mechanism:

A) At 2 years, the features listed above will independently predict a change in cognitive function. The statistical approach for this aim will be identical to that of the hypothesis in specific aim 1. Associations with cognitive

change scores and plaque area, volume, composition, microembolic counts, serum pro-inflammatory marker levels and cerebrovascular reactivity will be assessed using the mixed models of Laird and Ware106. Power to detect associations of cognitive decline with each of these features can be estimated using the same approaches as for the hypothesis in aim 1. We have used the most conservative approach of dichotomizing these continuous variables at their median value – the actual analysis will be performed using the variables as continuous measures where the power will be greater. Using this very conservative approach for power calculations, the same detectable differences in change score of 0.4 SD with 90% power, and of 0.3 SD with 80% power, are achievable.

B) At 2 years, patients with asymptomatic carotid stenosis who develop cognitive impairment will differ in these characteristics compared with similar patients that remain unchanged. The differential mean value for plaque area, volume, composition, microembolic counts, serum pro-inflammatory marker levels and cerebrovascular reactivity will be tested between the two groups using t-tests. The detectable difference for each of these factors is again very conservatively estimated to be the same differences of 0.4 SD with 90% power, and 0.3 SD with 80% power (now the SD of each of these factors). Such a small change relative to the SD of each of these factors is reasonable to define as being small enough to detect all “clinically important changes.”

Specific Aim 3 is designed to explore whether cognitive changes in patients with asymptomatic carotid stenosis correlate with changes in health-related quality of life. We hypothesize that at 2 years, regardless of plaque features, cognitive change will correlate with change in health-related quality of life measures.

For this aim, the principal outcome variables will be the change in quality of life measures (Frenchay and SF-36) between baseline and follow-up. The outcome event will be cognitive change score at the corresponding follow-up time point. Initially, the correlation between each quality of life change score and corresponding cognitive change score will be explored in a univariate fashion using t-tests. Subsequently, multivariate analysis will be used to determine the independent impact of altered cognition on quality of life after controlling for additional patient variables such as age, gender, mood, medical co-morbidities, and degree of stenosis. Independent predictors of change in quality of life will be selected based on $p \leq 0.05$. With the sample size of 142, a correlation of 0.2 between change in cognitive function and change in quality of life can be detected with 90% power, and a correlation of 0.18 can be detected with 80% power.

Potential difficulties and Alternate approaches/analyses:

Practice effect on cognitive testing. Since patients will be exposed to the same cognitive tests at different periods, scores may improve due to the “practice effect.” In this study, the practice effect is anticipated to be low since tests are being repeated at 1 year intervals (baseline, 1 year, and 2 years post-recruitment). Alternate test forms will be used wherever possible. Reliable change analyses will be used to determine if changes detected in the composite score, as well as on specific domain scores of interest exceed that which is expected based on repeated exposure to the measure, error variance, and maturation.

Additional analysis of Aim 1 including patients with post-recruitment stroke. Based on prior randomized trials, it is anticipated that approximately 1-2% of our patients per year will suffer a stroke2. Separating primary cognitive deficits from poor performance on cognitive testing due to disability associated with stroke is difficult. Furthermore, patients that develop stroke during follow-up will require carotid revascularization with elimination of the stenosis per standard of care. That is why the proposed study will exclude such patients when evaluating cognitive outcome. This attrition has been accounted for in the power analysis, and will not affect our results. Moreover, for those unable to complete testing due to stroke, the statistical E-M algorithm (Laird and Ware106) will be used to provide an estimate of the mean score in the presence of the missing data. This statistical approach has been shown to produce unbiased estimates that are more precise than alternative approaches in the presence of data that are missing.

Additional analysis of Aim 1 comparing baseline cognition in the two groups. We feel that a major strength of the application is the longitudinal data collection and comparisons of change scores. This is statistically much more powerful than a simple cross-sectional comparison. However, we will have data on baseline cognitive scores for patients versus control subjects. In an additional analysis we will perform a simple comparison of these scores to measure differences at baseline in the two populations.

Additional analysis of Aim 2 focusing on correlations with stroke during follow-up. For the patients in the cohort that suffer a stroke during follow-up, we will have plaque architecture, plaque composition, microembolic count, pro-inflammatory marker, and perfusion information, prior to their stroke. We are aware of the fact that the focus of our study is not on stroke; furthermore, these 5 to 10 patients will be too few to derive statistically strong conclusions. However, we will analyze available data and report additional conclusions on plaque correlates of stroke, if the information is hypothesis-generating.

TCD microembolic counts. We are aware that automated emboli counts and classifications are subject to the effectiveness of signal filtering algorithms. Therefore filters will be programmed according to criteria validated in consensus documents70. As an added precaution, we will analyze all spectral recordings manually to confirm embolic counts.

Temporal consistency. We are aware that the significance of outcomes and interpretation of mechanisms may be influenced by differential temporal effects. While the primary statistical approach will be to evaluate change scores over 2 years; we will describe the temporal pattern of cognitive changes and assess if the hypotheses are temporally consistent at the 1-year time interval.

Vascular risk factor distribution. We realize that the control group will include patients with a heterogeneous mix of one or more vascular risk factors. It is likely that one risk factor may have a larger influence on cognitive function than another; or multiple risk factors together in a patient may influence cognition more than in a patient with one risk factor. However, in a study of this size with finite resources, it will not be possible to expand the control group to the large numbers required to study the effects of each risk factor alone and in various combinations. In any case, that is well beyond the focus of this investigation. We will closely monitor the control subjects to ensure no unusual heterogeneity of cognitive scores. If such is found, we will then focus on recruiting patients with limited (one or two) risk factors alone.

**With regards to the planned additional follow-up, we will perform standard correlation analyses between cognitive scores of the subjects obtained previously with physical function scores that we plan to obtain during the additional follow-up.

ID: VIEW4E02806052800
Name: v2_Sample Size and Data Analysis

View: v2_Sharing of Results

Sharing of Results

- 1 * Describe whether results (study results or individual subject results, such as results of investigational diagnostic tests, genetic tests, or incidental findings) will be shared with subjects or others (e.g., the subject's primary care physicians) and if

so, describe how it will be shared:

Study results will not be distributed to the participants. However, subjects can request a copy of their results for their records. Additionally, study data will not be added to the patient's chart. If abnormal findings are discovered, the PI will refer the subject to the appropriate clinical service and share relevant information with them. The PI will personally approve each subject request.

**With regards to the planned additional follow-up, we will follow the same approach as described in the original protocol.

ID: VIEW4E02808CBD800
Name: v2_Sharing of Results

View: v2_Psychological/Behavioral/Educational Methods and Procedures

Psychological/Behavioral/Educational Methods & Procedures

You indicated on the "Type of Research" page that your study involves a psychological/behavioral/educational method or procedure such as a survey, questionnaire, interview, or focus group.

1 * Select all behavioral methods and procedures which apply to this study:

Surveys/questionnaires

Neuropsychological or psychophysiological testing

ID: VIEW4E09416F57800

Name: v2_Psychological/Behavioral/Educational Methods and Procedures

View: v2_Surveys/Questionnaires

Surveys/Questionnaires

You indicated that this study involves surveys and/or questionnaires.

If you uploaded a separate research protocol document in the 'Research Protocol' page, cite the applicable section and page numbers from that document in the answer boxes below.

1 * List all questionnaires/surveys to be used in the study, including both standardized and non-standardized assessments:

Original ACCOF protocol

Summary of Neurocognitive Tests: 1.Trail Making Test A & B, 2.Animal naming test, 3.Digit Span, 4.Digit Symbol-Coding, 5.Boston Naming Test-short form, 6.Hopkins Verbal Learning Test, 7.COWA oral word association test, 8.Rey Figure copy, 9.Brief Visuospatial Memory Test, 10.Grooved pegboard ("affected hand"), Grooved pegboard ("unaffected hand"),

Quality of Life Questionnaires: 1. SF 36 , 2. FAI

** With regards to the planned additional follow-up, we will perform the following tests:

Assessments of physical activity: 1) ABC, 2) FES, 3) PASE, 4) SF12,

Assessments of cognitive Health: 1) MMSE

2 * Upload a copy of all questionnaires/surveys:

Name	Created	Modified Date
ACCOF Mini Mental State Exam.pdf	6/9/2017 9:04 AM	6/9/2017 9:04 AM
ACCOF SF12.doc	6/9/2017 9:03 AM	6/9/2017 9:03 AM
ACCOF PASE.doc	6/9/2017 9:03 AM	6/9/2017 9:03 AM
ACCOF FES.doc	6/9/2017 9:03 AM	6/9/2017 9:03 AM
ABC	6/9/2017 9:03 AM	6/9/2017 9:03 AM
Animal naming test (neurocognitive test)	8/9/2010 11:28 AM	8/9/2010 11:29 AM
Neurocognitive tests	8/5/2010 12:59 PM	8/5/2010 12:59 PM
Quality of Life forms	7/22/2010 2:48 PM	7/22/2010 2:48 PM

3 * What is the total length of time that each survey is expected to take?

Original ACCOF protocol: Neurocognitive Battery tests will take 50 mins of time to complete. Quality of life tests will take 15 mins to complete

** With regards to the planned additional follow-up: Assessments of physical activity will take 20 minutes to complete; Cognitive Health assessment will take 5 minutes to complete.

4 * Are any of the questions likely to cause discomfort in participants or cause harm if their confidentiality were breached? (i.e., Illegal activities)

Yes No

5 * Do any questions elicit information related to the potential for harm to self or others?

Yes No

